1.4.2 Other Risks of Study Participation

There is the potential for loss of confidentiality for subjects participating in this study. However, every effort will be made to protect the confidentiality of subjects. After enrollment, patient identifiers will be linked to sequential numerical codes (Subject #1, #2, etc.). The detailed results of the research will be kept in a separate research file maintained by and accessible to only the investigators in a locked cabinet in [name] office. The numerical code key will also be maintained in a locked cabinet in [name] office and accessible only to investigators. If the patient is consented, and then withdraws from the study, their PHI will be discarded.

Furthermore, there is minimal risk of the electromyography (EMG) procedure. EMG is a noninvasive procedure which measures the compound muscle action potential (CMAP), experienced by the patient as a muscle twitch over the abductor pollicis brevis over the base of the thumb. EMG in this case will be measured by a surface electrode, which will be applied via an electrolyte gel and reinforced by tape. The patient may have a local allergic reaction to the gel and/or tape, which will be evaluated by the physician.

1.4.3 Potential Benefits

TMS is able to provide functional anatomy that can be used during surgical interventions and help in presurgical planning, potentially reducing the need for a more prolonged intraoperative mapping procedure. nTMS may be a useful adjunctive presurgical planning tool, in addition to other non-invasive

modalities including magnetoencephalography or functional MRI (fMRI). In addition, presurgical TMS mapping is also useful in planning the operative approaches and brain retraction and operative corridor (Najib 2011).

Because this is a feasibility study, results of nTMS motor mapping will not be presented as clinical information to surgeons in our study, therefore subjects may not benefit individually from this study. The ongoing practice during this study will be the use of DCS as standard of care. However knowledge gained from this study will benefit others in the future.

In particular, because TMS for motor mapping will likely result in generalizable knowledge which will benefit children and adolescents for future surgical planning (see page 2, Background section), we would like to include subjects from the ages of 12-17 years to establish validity in this population. Children and adolescents may benefit most from TMS mapping because their primary motor cortex is likely to have reorganized as a result of early brain injury and/or ongoing seizure activity (in some cases completely to the contralateral hemisphere), and who are less likely to tolerate other presurgical modalities such as functional MRI (fMRI) or magnetoencephalography (MEG).

The current study presents experiences which would be reasonably commensurate (or even less risk) with those expected in their actual medical evaluation for epilepsy surgery, most notably direct cortical stimulation for determination of functional cortex. The procedures would present no more than a minor increase over minimal risk, including the low possibility of an induced seizure (discussed on pages 4-5, under risks of investigational device), loss of confidentiality, and skin irritation from the EMG electrodes. There have never been reported any incidents of extreme pain, discomfort, stress or harm associated with single pulse TMS as described in our protocol. Any potential harm associated with TMS will be transient and reversible. To mitigate these minor risks, either [name] and [name], who regularly see children and adolescent on the outpatient and inpatient services (the latter while on call on the weekend) and who have specialty training in epilepsy, will be physically present during stimulation. However, to ensure maximum comfort and safety for children, the first 3 subjects run on this protocol will be adults (over 18 years old). Furthermore, to fully communicate the nature of these risks, adequate provisions are made for soliciting the assent of children and permission of their parents or legal guardians.

2 Study Objectives

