1.1 Background

Surgical treatment of focal epilepsy and motor mapping

Over 30% of epilepsy patients experience recurrent seizures despite the advent of new anti-epileptic medications (Kwan & Brodie 2000). Randomized controlled trials reveal that in appropriately selected surgical populations, epilepsy surgery can achieve superior outcome compared to continued medical therapy (Engel et al 2012).

Patients whose seizure foci are close to the motor cortex remain a challenge due to the potential risk of motor deficits after the surgery. Accurate mapping of the epileptogenic zone and surrounding cortical area is used to guide maximal resection of the epileptogenic cortex while avoiding unacceptable damage to eloquent cortex. **Currently intra-operative direct current stimulation (DCS) is the gold standard, and is the clinical standard of care for surgical planning.** If epileptogenic cortex and putative resection site is close to eloquent cortex. A subdural grid is implanted for intracranial EEG monitoring and seizure foci localization. After enough interictal or ictal events are captured, the patient will have functional mapping while in close monitored EMU setting.¹

However, noninvasive functional mapping of motor cortex, via TMS and other non-invasive modalities such as fMRI or MEG, would optimize presurgical planning and patient counseling. In addition, in some cases, presurgical evaluation could determine whether a surgical resection is feasible, or whether the patient would be a better candidate for another procedure such as responsive neurostimulation (RNS) or vagal nerve stimulation (VNS) which would spare overlapping eloquent cortex. Furthermore in the pediatric epilepsy population, presurgical motor mapping by TMS may determine that motor and other eloquent cortex has completely reorganized (sometimes to the contralateral hemisphere), such that surgical resection of the epileptogenic cortex would be unlikely to cause a functional deficit.

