3.1.1 Baseline clinical visit and seizure diary

We will enroll 14 patients who will undergo epilepsy surgery with expected subdural grid coverage over primary motor cortex. Potential subjects will be identified at the weekly multi-disciplinary epilepsy conference. Subjects must have a recent (<2 years) MRI scan, and registration of the TMS coil to the MRI scan via the Brainsight neuronavigation system will be utilized to guide TMS coil placement (Gugino et al 2001). When a presurgical fMRI is available which demonstrates the patient's hand knob, the fMRI will be used with the Brainsight neuronavigation system. Subjects will be recruited and consented during a presurgical clinical visit where the patient's primary epileptologist will introduce members of the research team.

Patients will be asked to keep a 7 day seizure diary prior to the TMS session.

3.1.2 nTMS mapping

Patients will receive a session of single-pulse TMS mapping of the motor area, at the outpatient TMS clinic at NYU Neurology Ambulatory Care Center, at [name] prior their epilepsy surgery, according to the following procedures:

- a. Determination of the motor threshold by (1) finding the most excitable region in the hand knob which elicits the strongest compound muscle action potential (CMAP) in the APB muscle; (2) finding the motor threshold by determining output stimulation intensity which generates peak to peak CMAP response above 50 mV in 5/10 stimulation cycles (Rossini et al., 1994).
- b. Concurrent EMG will be measured with electrodes placed at APB, abductor digiti minimi, flexor carpi radialis muscles. Reference electrode will be placed at the ipsilateral elbow above the brachial biceps muscle.
- c. Mapping of the upper extremity. After determination of the MT, mapping of the UE will be performed at 110% of the rMT. All positive and negative stimulation sites will be recorded and saved.

Patients will be closely monitored during TMS stimulation. Each subject will have a complete neurological examined by a neurologist before and immediately after nTMS. Patients will also be provided a side effects questionnaire after TMS mapping. Patients will then be asked to keep a 7 day seizure diary after the nTMS session

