7.1 Sample Size Determination

We estimate 10 subjects total necessary to detect a 50% difference between nTMS and DCS mapping, assuming alpha 0.05 and power 0.8. However, given the possibility of subject dropout, and the unknown nTMS side-effect profile and seizures we propose to add ~1/3 to total patient enrollment, and thus will enroll 14 patients. We plan to enroll at least 4 children ages 12-17 years, to assess for the validity of nTMS in a pediatric population, which is expected to benefit the most from this procedure.

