7.3 Subject Population(s) for Analysis

All subjects who complete the nTMS motor mapping session and later undergo direct cortical stimulation for functional mapping will be included in the analysis.

8. Safety and Adverse Events

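### Section 7.3 analyses only subjects who complete nTMS mapping, so agreement is conditional on a map having been obtained, and a DCS-confirmed absence of hand cortex goes unscored

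*Combined protocol and SAP*

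**What the plan says.** **Why children are enrolled.** Section 1.4.3 says of them that "their primary motor cortex is likely to have reorganized as a result of early brain injury and/or ongoing seizure activity", and adds "in some cases completely to the contralateral hemisphere". Section 1.1 names the clinical use: "presurgical motor mapping by TMS may determine that motor and other eloquent cortex has completely reorganized". Section 7.1 plans at least 4 children "to assess for the validity of nTMS in a pediatric population, which is expected to benefit the most from this procedure".

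**How a map is made.** Section 3.1.2, item a, starts by "finding the most excitable region in the hand knob which elicits the strongest compound muscle action potential" in the APB muscle, then by "finding the motor threshold by determining output stimulation intensity which generates peak to peak CMAP response above 50 mV in 5/10 stimulation cycles". Item c follows: "After determination of the MT, mapping of the UE will be performed at 110% of the rMT". Section 5.2 places the resting threshold at the hand hotspot. Neither section says what happens if no hand response is found or if 110% of threshold cannot be delivered. Positive and negative sites are both saved.

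**What is analysed.** Section 7.3 takes "All subjects who complete the nTMS motor mapping session and later undergo direct cortical stimulation" for functional mapping. It does not define completion. Section 3.2 lists (a) distance between positive DCS and nTMS sites, (b) site-level concordance giving predictive values, and (c) distance to fMRI sites. Section 7.2 works from averaged positive nTMS sites and a same-gyrus rule, and gives no method for the predictive values. Sections 1.4.1 and 8.1 stop mapping for the day after certain seizures, but nothing says how such a session counts under 7.3.

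**The concern.** nTMS is the test under evaluation and DCS is the reference. If subjects in whom the test yields no map are left out, the agreement that remains describes nTMS only where it worked. A surgeon reading the result needs to know how often it does not work. Sections 1.1 and 3.1 call this a feasibility study, yet no endpoint counts maps that could not be obtained, and section 7.1 treats losses as something to be offset by enrolling more subjects.

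The paediatric rationale sharpens this. If hand function has moved out of the tested hemisphere, the correct nTMS finding is that no hand response can be elicited there, and DCS can confirm or refute it. The plan has no place to record that as agreement, nor to record the opposite case (no nTMS response, but a DCS hand site) as a failure. With inclusion hanging on an undefined word, the choice could also be made after the results are known.

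**Working it through.** **1. The plan's own figures.** Section 7.1 estimates 10 subjects and adds about one third: 10 × 4/3 = 13.3, rounded up to 14. The 10 cannot be verified because the test, scale, SD and sidedness are not stated; nothing below depends on it. The allowance for loss is 14 − 10 = 4, so up to four missing maps would fit inside it.

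**2. Where each kind of subject goes.** Assumed, because the documents do not say: nTMS is applied to the hemisphere to be implanted.

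| Situation | Section 7.3 | Distance and gyral rule (7.2) | Predictive values (3.2b) |
|---|---|---|---|
| No hand response, DCS hand-positive | out on the natural reading | not computable: no nTMS site | unclear: no threshold, so no defined intensity |
| No hand response, DCS hand-negative | out on the natural reading | not computable: no site in either method | unclear, same reason |
| Threshold found, 110% not deliverable | out on the natural reading | no map at the stated intensity | unclear |
| Session stopped early | depends on the meaning of completion | possible only if positive sites were already found | unclear |
| Map finished, but site misplaced or falsely negative | in | counted if a positive site exists | counted |

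The third row applies when the threshold exceeds 100/1.10 = 90.9% of maximum stimulator output.

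**3. Size, as an assumed illustration.** Suppose all 14 start nTMS and undergo DCS, k have no map, and every mapped subject is concordant at patient level. Completers give (14 − k)/(14 − k). Counting each missing map against nTMS gives (14 − k)/14. Intervals are exact (Clopper-Pearson) 95%.

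| k | Completers only | All 14, each missing map counted against nTMS |
|---|---|---|
| 1 | 13/13 = 100% (75 to 100) | 13/14 = 93% (66 to 99.8) |
| 2 | 12/12 = 100% (74 to 100) | 12/14 = 86% (57 to 98) |
| 4 | 10/10 = 100% (69 to 100) | 10/14 = 71% (42 to 92) |

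If every missing map were instead an absence of hand cortex confirmed by DCS, all 14 would agree. The completers-only figure is 100% in both situations and cannot tell them apart.

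For 4 children the same arithmetic gives 3/3 = 100% (29 to 100) against 3/4 = 75% (19 to 99) with one missing map, and 2/2 = 100% (16 to 100) against 2/4 = 50% (7 to 93) with two.

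**4. How likely is at least one such child?** The documents give no rate f of absent hand response. For 4 children the chance is 1 − (1 − f)^4. At assumed rates of 5%, 10%, 20%, 30% and 50% it is 19%, 34%, 59%, 76% and 94%.

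**The case against.** Several stronger readings are tempting, and the documents do not support them.

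- **That 7.3 expressly drops non-responders.** It does not. A child who attends and yields only negative sites could be called a completer and enter the predictive values. This stands as a limit: exclusion is the natural reading, not a written rule. It does not rescue the plan, because the distance and gyral analyses still need a positive nTMS site, and the negative sites would have no specified intensity.
- **That all nTMS failures vanish.** Misplaced, false-positive and false-negative sites within a map stay in. Only failure to obtain or finish a map is at risk.
- **That the paediatric question cannot be answered.** Section 1.4.3 claims complete transfer for some cases only. Section 5.2 locates the hand area by a free search for the largest response, and 3.1.1 brings in fMRI where available, so partial or within-hemisphere reorganization may still give a map. Section 1.4.3 also includes children because they may tolerate fMRI or MEG poorly, and that reason is untouched.
- **That the data are thrown away.** DCS sites and nTMS sites are recorded, and section 9.3 requires missing data to be explained. What is missing is the analysis rule.
- **That 7.3 is what blocks the distance endpoint.** In a fully transferred hemisphere DCS should show no hand site either, so no choice of population makes a distance computable.

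It is also fair to object that scoring every no-response as a negative would credit technical failures as agreement whenever DCS is negative. That objection stands, and the fix below keeps such cases separate.

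**Conclusion.** The concern holds in limited form. Mapping depends on a threshold that needs a hand response, there is no fallback, and the analysis set is restricted to completers. Agreement is therefore likely to be reported conditional on nTMS having produced a map, and an absence of hand cortex confirmed by DCS, which the protocol itself presents as a paediatric use, is not scored.

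The direction favours nTMS where missing maps are true failures. The amount is unknown: 100% against 93% to 71% is an illustration resting on 1 to 4 unmapped subjects among 14, full concordance in the rest, a patient-level measure, and every missing map counting against nTMS. The plan should be changed, but this does not undermine the comparison in subjects who have a map.

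**What to change.** 1. In 7.3, define the mapping population as all subjects who start the nTMS session and undergo DCS, and define when a session counts as complete.
2. Report the number of missing or unfinished maps, with the reason for each, as a feasibility outcome.
3. Keep distances limited to subjects with positive sites in both methods.
4. Report patient-level concordance with no-response as its own category, cross-classified against DCS: hand-positive, or hand-negative with the hand area covered by electrodes. Add two sensitivity analyses: one counting all no-response cases against nTMS, and one counting DCS-confirmed absences as agreement.
5. Report undeliverable 110% of threshold and stopped sessions as technical failures, not as negatives.
6. State in 7.2 whether sites stimulated without a threshold enter the predictive values, and state beforehand what will be recorded as no hand response. How the search is carried out is for the investigators.
7. If no child with an absent hand response is observed, limit the paediatric conclusion to children with a mappable hand area in the implanted hemisphere.

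Cost: wording and case report form entries, with no added visit or patient. The headline agreement may fall and the paediatric claim may narrow.

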2.1 Primary Objective

We propose a phase 1 clinical trial to examine the degree of concordance between neuronavigation guided TMS (nTMS) and direct cortical stimulation (DCS) in identifying hand motor cortex in adults and children undergoing epilepsy surgery.

2.2 Secondary Objective(s)

This trial is also designed to detect safety and tolerability of nTMS in epilepsy patients.

3 Study Design

3.1 General Design and Study Protocol

This study will be an open-label feasibility study which applies nTMS to subjects with incoming epilepsy surgery and pre-surgical motor mapping. No study-related medication changes are expected -- participants will remain compliant with their regular anticonvulsant regimen throughout each study phase. All patients will have undergone a complete history and neurological exam as part of their routine clinical care at the NYU Comprehensive Epilepsy Center.

The phases described in detail below are as follows:

Phase	Description	Duration
Baseline	Informed Consent and baseline neurological visit, instructions for maintaining a seizure diary	30 min-1 hours
1	nTMS mapping	2 hours
2.	Follow-up clinical visit after the surgery	30 minutes

3.1.1 Baseline clinical visit and seizure diary

We will enroll 14 patients who will undergo epilepsy surgery with expected subdural grid coverage over primary motor cortex. Potential subjects will be identified at the weekly multi-disciplinary epilepsy conference. Subjects must have a recent (<2 years) MRI scan, and registration of the TMS coil to the MRI scan via the Brainsight neuronavigation system will be utilized to guide TMS coil placement (Gugino et al 2001). When a presurgical fMRI is available which demonstrates the patient's hand knob, the fMRI will be used with the Brainsight neuronavigation system. Subjects will be recruited and consented during a presurgical clinical visit where the patient's primary epileptologist will introduce members of the research team.

Patients will be asked to keep a 7 day seizure diary prior to the TMS session.

3.1.2 nTMS mapping

Patients will receive a session of single-pulse TMS mapping of the motor area, at the outpatient TMS clinic at NYU Neurology Ambulatory Care Center, at [name] prior their epilepsy surgery, according to the following procedures:

- a. Determination of the motor threshold by (1) finding the most excitable region in the hand knob which elicits the strongest compound muscle action potential (CMAP) in the APB muscle; (2) finding the motor threshold by determining output stimulation intensity which generates peak to peak CMAP response above 50 mV in 5/10 stimulation cycles (Rossini et al., 1994).
- b. Concurrent EMG will be measured with electrodes placed at APB, abductor digiti minimi, flexor carpi radialis muscles. Reference electrode will be placed at the ipsilateral elbow above the brachial biceps muscle.
- c. Mapping of the upper extremity. After determination of the MT, mapping of the UE will be performed at 110% of the rMT. All positive and negative stimulation sites will be recorded and saved.

Patients will be closely monitored during TMS stimulation. Each subject will have a complete neurological examined by a neurologist before and immediately after nTMS. Patients will also be provided a side effects questionnaire after TMS mapping. Patients will then be asked to keep a 7 day seizure diary after the nTMS session

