A neurostimulation technique, navigated transcranial magnetic stimulation (nTMS) is a potentially valuable tool for preoperative motor mapping. Previously there have been several studies to test the accuracy of TMS to DCS, and in comparison with other noninvasive modalities, including magnetoencephalography (MEG) and functional MRI (fMRI) (Najib 2011; Romero 2011, Tarapore 2012, Krieg 2012), suggesting that nTMS can have an extremely high degree of functional accuracy, identifying primary motor cortex within 2 mm of accuracy, and with a high positive and negative predictive value (Tarapore 2012).

A similar neuronavigated device, the integrated Nextstim device manufactured by Neurostar, was FDA approved for presurgical motor mapping in 2009 (Please see appendix). We are testing the Magstim Rapid² TMS coil and Brainsight Neuronavigation system (instead of the Nextstim) because the dual system allows co-registration to the patient's structural MRI, functional MRI(fMRI) or EEG. Furthermore,

¹ Electrical stimulation of the cerebral cortex will be conducted utilizing a NicoletOne Cortical Stimulator which delivers a constant current output. The stimulus parameters are set to a pulse width of 500 microseconds, pulse frequency of 50 Hertz and maximum train duration of 5 seconds. The stimulus current is manually controlled during the stimulation and ranged from 1 mA to 12 mA. Stimulation is applied to adjoining electrode pairs. Responses are confirmed with repeat stimulation and testing at the initial pair and with adjoining electrodes when necessary. Electrical stimulation is started at 1 mA and gradually increased in increments of 1-4 mA until a maximum of 12 mA was achieved or until after-discharges are seen or a functional response is observed. Positive and negative functional sites will be recorded.

the dual system is a more flexible system for other research use with other stimulation devices (such as transcranial direct current stimulation and simultaneous EEG recording) and robotic devices.

We propose an open-label feasibility study to test the accuracy of nTMS to the gold standard DCS, as well as to fMRI (an adjunctive presurgical planning tool), in determining both positive and negative motor sites, and correlate with clinical outcomes.

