Magnetic fields attenuate rapidly with distance, so it seems unlikely that the fetus might be directly affected by TMS. There are anecdotal reports of pregnant women who underwent successful rTMS

treatment for depression, and no side effects to the child were reported (Nahas et al., 1999; Klirova et al., 2008; Ross 2007). Nevertheless, the effects of the TMS device on the reproductive system (sperm, eggs) or to the developing fetus are unknown. For this reason, pregnant patients will be excluded from participation in this study.

As evidence of safety, the **Nexstim TMS system**, which provides exactly the same type of single TMS described here, is approved for use as a tool to perform mapping of motor cortex in patients with neurological disorders of all ages (December 2009, FDA approval notice K091457), for pre-surgical planning (for example, in epilepsy patients and in brain tumor patients). The Magstim Rapid² is developed and manufactured in accordance with US 21 CFR 820 and is cleared in the USA under 510(k) number K051864 for the stimulation of peripheral nerves. However, unlike the Nexstim system, which is fully integrated with a built in-neuronavigation system, the neuronavigation system (Brainsight) compatible with Magstim permits targeted neuronavigation with MRI layered with fMRI, EEG, or NIRS (near infrared spectroscopy), permitting greater research flexibility and other modalities of validating motor and other eloquent function.

TMS Advantages: In this study, TMS is safe, non-invasive, and offers a potentially useful adjunctive test for presurgical planning. The stimulation coil can be easily placed precisely on interested cortical surface with guidance of anatomical scans. TMS session does not interfere with other treatment or diagnostic tests.

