3.2 Primary Study Endpoints

The trial is designed to detect strength of spatial correlation between topographic maps of hand motor representation obtained through noninvasive nTMS compared to direct, extra-operative cortical stimulation obtained as part of usual clinical evaluation during epilepsy surgery, as measured by (a) average distance between positive motor mapping sites of DCS compared to nTMS and (b) degree of concordance between positive and negative motor mapping sites between DCS and nTMS, to generate positive and negative predictive values, and (c) average distance between positive motor functional sites of fMRI compared to nTMS.

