5.1 Description

Preoperative mapping was performed with **Magstim Rapid²** (Magstim) brain stimulation system. It delivers a biphasic TMS pulse from a figure-of-eight coil with an outer diameter of 70 mm. The system calculates the strength, location, and direction of the stimulating electric field in cortical tissue and takes the subject's head size and shape into account. The estimates of the induced electric field are based on a dynamic spherical model adjusted in real time and the physical parameters of stimulation.

Brainsight Navigation,(Rogue Resolutions) will provide the hardware and software environment to guide TMS application in a manner which is co-registered to the patient's MRI Brain. With combined use of the Magstim Rapid2 and Brainsight, the TMS coil can be navigated and positioned over a specified target location based upon the MRI Brain, thereby directing the stimulation in a spatially precise manner.

Neither the Magstim Rapid2 or Brainsight are FDA approved. However, the combination of **Magstim Rapid²** and **Brainsight NeuroNavigation** system is comparable to the Nextstim TMS system, which was FDA approved in 2009 for use in presurgical motor mapping (see attachment). Brainsight NeuroNavigation system is a non-significant risk device, as there it represents an imaging tool complementary to the TMS machines, and does not make contact with the patient.

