5.2 Treatment Regimen

TMS with brief single pulse sequence and 3-4 seconds interval between pulses will be used in motor mapping in our study. The hand knob will be determined by free point to point stimulation as the location eliciting the largest MEP Reponses form the muscle interested, The resting motor threshold (rMT) was determined at the hand hotspot. rMT is defined as minimal stimulation intensity capable of generating an MEP in 50% of cases. Muscle representation areas relevant for clinical decisions were mapped with an intensity of 110% of rMT. Cortical muscle presentation areas were stimulated by an induced electric field orientated perpendicular to the central sulcus. The stimulation coil was hold tangential to the scalp. The tilt will be monitored on-line and adjusted so as to produce the strongest field strength in the cortex.

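### Primary endpoint (c), the nTMS-to-fMRI distance, is not clearly independent, because the same fMRI may be in the navigator while nTMS is mapped

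*Combined protocol and SAP*

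**What the plan says.** Section 3.1.1 gives Brainsight, registered to the subject's MRI, the task of guiding coil placement. The next sentence reads: "When a presurgical fMRI is available which demonstrates the patient's hand knob, the fMRI will be used with the Brainsight neuronavigation system". It does not say whether the fMRI sets targets, is displayed as an overlay during mapping, or is loaded only for later comparison.

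Section 3.2 lists three primary measures. The third is "c) average distance between positive motor functional sites of fMRI compared to nTMS". Section 1.1 presents the fMRI comparison, alongside DCS, as a test of nTMS accuracy.

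The device sections point in both directions:

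- Section 1.1 justifies this system partly by co-registration to "structural MRI, functional MRI(fMRI) or EEG", and section 1.2 says it "permits targeted neuronavigation with MRI layered with fMRI, EEG, or NIRS".
- Section 5.1 describes the target from the MRI alone: "the TMS coil can be navigated and positioned over a specified target location based upon the MRI Brain".
- Section 5.2 defines the nTMS site physiologically: "The hand knob will be determined by free point to point stimulation as the location eliciting the largest MEP".
- Section 3.1.2 places the hotspot search in the hand knob and adds: "All positive and negative stimulation sites will be recorded and saved".

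Section 7.2 gives distance calculations for nTMS against DCS. It does not mention fMRI, so (c) has no stated calculation.

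**The concern.** A distance between two methods is evidence of accuracy only if neither method helped to locate the other. If the operator can see the fMRI hand area while choosing where to stimulate, stimulated sites may cluster around it. EMG then sorts those sites into positive and negative, but it cannot register a positive site that was never stimulated. The averaged nTMS position can therefore move towards the fMRI site, and (c) becomes shorter for a reason unrelated to accuracy.

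The instruction applies whenever a suitable fMRI exists, so the subjects who supply (c) are essentially those with the fMRI in the navigator. That leaves no unassisted group against which to check (c). A short distance would still be read as one of three primary indications that nTMS is accurate.

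**Working it through.** The plan gives no figure for (c), so there is none to reproduce. The check has two parts.

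**1. Do the passages close the route?** Four statements would do so: that the fMRI is loaded only after mapping, that it is hidden from the operator, that the search area is fixed without it, or that mapping continues until negative sites surround the positive zone. None appears in sections 1.1, 1.2, 3.1.1, 3.1.2, 3.2, 5.1, 5.2 or 7.2. Limiting the hotspot search to the hand knob is not such a safeguard, because that is the structure the fMRI is selected for showing. The physiological definition in 5.2 limits the dependence but does not remove it.

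**2. How large could the effect be?** All inputs below are assumptions; the documents give no search area, map size or fMRI error.

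*Truncation model.* The fMRI site is at the origin. The EMG-positive zone is a disc of radius r centred at distance d. Stimulation covers a disc of radius R around the fMRI site. The recorded nTMS position is the centroid of the overlap (site averaging, borrowed from the nTMS-DCS rule in 7.2), and (c) is its distance from the origin. Without truncation (c) = d, and there is no bias once R ≥ d + r. As a hand check, with r = d = R = 10 mm the overlap is symmetric about the midpoint, so (c) = 10/2 = 5.0 mm.

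Numerical results for r = 10, d = 10 mm:

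| R (mm) | (c), fMRI-centred (mm) | Shortening | Mean (c), MRI-only (mm) |
|---|---|---|---|
| 5 | 2.3 | 77% | 11.5 |
| 7.5 | 3.6 | 64% | 11.0 |
| 10 | 5.0 | 50% | 10.6 |
| 15 | 7.8 | 22% | 10.1 |
| ≥ 20 | 10.0 | 0% | 10.0 |

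The last column centres the same disc on an anatomical guess 10 mm from the true centre, averaged over all directions. If that guess errs exactly towards the fMRI site, the shortening equals that of fMRI centring (5.0 mm at R = 10).

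Other inputs, fMRI-centred:

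- r = 5, d = 10: (c) is 6.3 mm at R = 7.5, 7.7 at R = 10, and 10.0 from R = 15.
- r = 10, d = 15: (c) is 7.5 mm at R = 10, 10.2 at R = 15, and 15.0 from R = 25.

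*Shrinkage model.* Let nTMS and fMRI have independent two-dimensional errors with SD s_T and s_F per axis, and let the recorded nTMS site be pulled a fraction w towards the fMRI site. Then:

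- mean nTMS-fMRI distance = √(π/2) × (1 − w) × √(s_T² + s_F²)
- mean nTMS error against truth = √(π/2) × √((1 − w)² s_T² + w² s_F²)

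With s_T = s_F = 5 mm, the first is 1.253 × 7.07 = 8.9 mm at w = 0, then 6.6, 4.4 and 2.2 mm at w = 0.25, 0.5 and 0.75. The true error is 6.3, 4.9, 4.4 and 4.9 mm. With s_F = 10 mm, (c) falls from 14.0 mm at w = 0 to 3.5 mm at w = 0.75, while the true error rises from 6.3 to 9.5 mm. So (c) can improve while localisation gets worse. The real w is unknown and may be near 0.

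**The case against.** The strongest reply is that the instruction is ambiguous. Computing (c) requires both maps in one coordinate system, so loading the fMRI into Brainsight may mean no more than that. The sentence is in the baseline section, the mapping steps in 3.1.2 contain no fMRI step, 5.1 bases the target on the MRI, and 1.2 also mentions validation as a use of the layered images. Positivity is decided by EMG on three muscles, negative sites are saved, and no text says mapping stops early. This stands as a limit on size: dependence is possible, not shown. It does not restore independence, because the sentence directly follows the one on coil guidance and 1.2 describes layered fMRI as a way of targeting.

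Second, truncation around an anatomical guess could also shorten (c) if anatomical and fMRI errors point the same way. This is a fair criticism of the MRI-only column above, which assumes independent directions. If the anatomical error lies within ±45° of the fMRI direction, mean MRI-only (c) is about 4.5, 5.1, 5.9 and 8.1 mm at R = 5, 7.5, 10 and 15 (to within about 0.1 mm, depending on the directions sampled). Much of the shortening then comes from truncation itself, but fMRI centring still gives the shorter value at each R (2.3, 3.6, 5.0 and 7.8 mm).

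Third, the objective, sample size and section 7.2 concern DCS, and this is a 14-subject feasibility study in which fMRI is adjunctive. That is true and limits the consequence, but (c) is still listed as primary.

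**Conclusion.** The concern holds as a moderate one that should be fixed. As written, the plan allows the fMRI to influence which sites are stimulated and then treats closeness to that fMRI as a primary measure of nTMS accuracy. Endpoint (c) is therefore not clearly independent evidence and may be biased towards agreement by an unknown amount. In the truncation example the shortening runs from 0% (R of 20 mm or more) to 77% (R of 5 mm), with every input assumed. These figures show direction and the condition for no bias; they do not estimate this trial's bias.

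The conclusion does not extend to calling (c) invalid. Endpoints (a) and (b) keep an independent reference, since DCS does not depend on this route and "results of nTMS motor mapping will not be presented as clinical information to surgeons in our study". In subjects mapped with the fMRI visible, however, (a) and (b) describe fMRI-assisted nTMS. The sample size is unaffected.

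**What to change.** **Preferred.** State in 3.1.1 that nTMS mapping is navigated on the structural MRI, that all positive and negative sites are saved and locked, and that the fMRI is loaded only afterwards to compute (c).

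**Alternative.** If the fMRI stays visible during mapping, record this for each subject, report (c) as exploratory and not independent, and describe (a) and (b) in those subjects as results for fMRI-assisted nTMS. This also requires an edit to 3.2.

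**In either case.** Use the saved sites to report, for each subject, whether the positive zone was bounded by negative sites; where it was, this route does not shorten (c). Define bounded in 7.2.

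**Cost.** A sentence in 3.1.1, one case report form item, one descriptive check on data already kept, and the small edits to 3.2 and 7.2. No scan or visit is added, since every subject already needs a structural MRI. The hotspot search may take longer within the 2-hour session, and under the preferred option fMRI-layered navigation, a stated reason for choosing this system, is not used during mapping. Withholding the fMRI from the navigator does not blind an operator who saw it at the surgical conference. Full blinding might need another team member and is not requested. The change has to precede mapping, because an independent map cannot be recovered from a session run with the fMRI in view.
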